2.4.2 Prior, concomitant and post therapies

Prior and concomitant medications will be summarized by the treatment group and overall, in separate tabulations based on the coding dictionary used. Medications will be presented using the preferred drug names and grouped by anatomical main group. Tables will show the number and percentage of participants receiving at least one drug of a particular preferred drug name and at least one drug in a particular anatomical main group. Significant non-drug therapies will be summarized in a similar way, using the PTs and grouped by primary SOC.

Prior medications and significant non-drug therapies are defined as any medications and significant non-drug therapies taken and stopped prior to the first administration of study treatment (Day 1). Concomitant medications and significant non-drug therapies are defined as those used during the

double-blind period, including those that started before or on Day 1 and are either ongoing or stopped on Day 1 or later, as well as those that started after Day 1.

In addition, LLTs added after Day 1 will be presented using the preferred drug names and summarized by the treatment group and overall. LLTs added after Day 1 are defined as concomitant medications with 2nd level ATC classification being C10 (lipid modifying agents) and start date after Day 1 date.

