**Table 6-3 Prohibited medication**

Class of medication	Prohibition period	Action taken
LLT [statins, ezetimibe (other than control drug), bempedoic acid, psyllium preparations, fibrates, bile-acid sequestrants, red yeast rice, niacin > 200 mg/day, omega-3 fatty acids (DHA and/or EPA with a total dose > 1000 mg/day)], or any drug with unknown ingredients taken for the purpose of lipid-lowering, including over-the-counter or herbal therapies	At least 90 days prior to screening and until randomization  Randomization and throughout the study	Do not randomize the participant  Ask participants to stop taking LLTs. Contact Novartis for further guidance.
Systemic cyclosporine and tacrolimus Systemic steroids Vitamin A derivatives or retinal derivatives for the treatment of dermatologic conditions (vitamin A in a multivitamin preparation is permitted)	At least 30 days prior to screening and until randomization	Do not randomize the participant
Antiviral therapies (protease inhibitors or direct acting antivirals)	Randomization and throughout the study	Contact Novartis for further guidance.
Investigational drugs Any RNAi-based therapeutics, including but not limited to siRNA or ASO Therapies	At least 30 days or 5 half-lives, whichever is longer, prior to screening and until randomization  Randomization and throughout the study	Do not randomize the participant  Discontinue study treatment
Monoclonal antibodies directed towards PCSK9 such as evolocumab and alirocumab	At least 90 days prior to screening and until randomization  Randomization and throughout the study	Do not randomize the participant  Discontinue study treatment

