### Prior and concomitant therapies

Prior or concomitant medications will be summarized for the SAF in separate tabulations based on the coding dictionary used. Medications will be presented in alphabetical order, by preferred terms and grouped by anatomical main group, according to the ATC classification system. Tables will show the overall number and percent of participants receiving at least one drug of a particular preferred term and at least one drug in a particular anatomical main group.

Prior medications and significant non-drug therapies are defined as any medications and significant non-drug therapies taken prior to the randomization visit. Concomitant medications and significant non-drug therapies are defined as those used during the double-blind period. Concomitant medications that were prohibited as per protocol and given during the conduct of the study as well as significant non-drug therapies will be summarized.

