2.3 Patient disposition, demographics and other baseline characteristics

2.3.1 Patient disposition

The following participant disposition at screening and randomization will be summarized by treatment group and overall, for the SCR:

- Screened (Screened Set)
 - Completed screening
 - Did not complete screening
 - Reasons for not completing screening
- Randomized (Randomized Analysis Set)
- Included in the Full Analysis Set
- Treated (Safety Analysis Set)

The following study treatment disposition will be summarized by treatment group and overall, for the SAF:

- Completed study treatment
- Discontinued study treatment prematurely
 - Primary reason for early discontinuation of study treatment

The following study disposition will be summarized by treatment group and overall, for the RAS:

- Completed study
- Discontinued prior to study completion
 - Primary reason for discontinuing study

The duration of study (number of days from Day 1 to the date of last contact/participation date) will be summarized using descriptive statistics by treatment group and overall, for the FAS.

The frequency (%) of participants with protocol deviations will be presented for the RAS. Finally, the number of randomized participants by region (Latin America, Europe, USA) and country will be presented descriptively for the RAS.

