3.2 Secondary endpoints

Statistical power will not be assessed for secondary endpoints.

4 Change to protocol specified analyses

No change from protocol specified analysis was made.

5 Appendix

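### Do the SAP's missing prohibited-medication summary and its silence on stopped LLT courses call for a change to the plan?

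*SAP*

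**What the plan says.** **Medication summaries.** Protocol 12.3, under prior and concomitant therapies, commits to summarizing "Concomitant medications that were prohibited as per protocol and given during the conduct of the study". SAP 2.4.2 does not repeat this. It plans prior and concomitant medication tables by drug name and anatomical main group, a matching table of non-drug therapies, and a table of LLTs added after Day 1, "defined as concomitant medications with 2nd level ATC classification being C10 (lipid modifying agents) and start date after Day 1 date". SAP 2.3.1 adds: "The frequency (%) of participants with protocol deviations will be presented for the RAS".

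**Prior medication.** Protocol 12.3 counts medications and "significant non-drug therapies taken prior to the randomization visit". SAP 2.4.2 requires that they were also stopped, and it uses the first dose as the reference point.

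**Declaration.** SAP Section 4 states: "No change from protocol specified analysis was made".

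**LLT during the study.** For most LLTs taken after randomization, Protocol Table 6-3 instructs sites: "Ask participants to stop taking LLTs. Contact Novartis for further guidance". SAP 2.5.3 treats LLT use in the Monotherapy Estimand under a hypothetical strategy in which no other LLT is available. Efficacy values after the intercurrent event are multiply imputed under missing-at-random (MAR).

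**The concern.** Two things look wrong.

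First, the protocol promises an output that the SAP does not list, the SAP alters a definition, and Section 4 says nothing was altered. The LLT table is not a substitute. It covers lipid-modifying agents only, while Table 6-3 also prohibits systemic steroids, cyclosporine, tacrolimus, vitamin A or retinal derivatives, antivirals, investigational drugs and RNAi-based therapeutics. A class code with a start date also cannot apply the table's dose limits ("niacin > 200 mg/day, omega-3 fatty acids (DHA and/or EPA with a total dose > 1000 mg/day"). At stake is traceability: a reader of the study report would find no table that marks which drugs were prohibited.

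Second, because sites ask participants to stop an added LLT, some may reach Day 150 well after a short course while still on randomized treatment. Protocol 12.4.3 leaves details to the SAP, yet SAP 2.5.3 never mentions this case and cites no product list. If one analyst kept the observed Day 150 value and another imputed it, one of the two primary estimands would depend on an unstated choice. Neither sensitivity analysis in SAP 2.5.5 varies that choice.

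**Working it through.** **1. What the missing summary would add.**

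| Item | Protocol 12.3 | SAP |
|---|---|---|
| All concomitant medications by arm | Planned | Planned (2.4.2) |
| Prohibited medications, identified as such | Planned, format not specified | Not listed |
| Added LLT by arm | No separate table | Planned (2.4.2) |
| Protocol deviations | Planned (Protocol 12.2) | Planned (2.3.1) |

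Every recorded prohibited drug is counted by drug name and arm in the general table; only the label is missing. The class most relevant to LDL-C, added LLT, has its own table. Medications are recorded throughout the study, so the protocol's summary can be produced without new data.

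**2. The changed definition.** The SAP wording separates prior from concomitant use, so that a drug continued past Day 1 is counted as concomitant. It governs descriptive tables only and enters no efficacy model.

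**3. Whether SAP 2.5.3 leaves a stopped course open.**
- Trigger: use of LLT, with no condition on duration or continuation.
- Consequence: efficacy values after the event are imputed.
- Reference group for the MAR imputation: same-arm participants with the same covariates and no intercurrent event. Someone who took and stopped an LLT is not in that group.
- Start: the protocol glossary limits intercurrent events to those after treatment initiation, and Table 6-3 bars randomization after recent LLT use. Only the ordering of a same-day Day 1 start is left.
- Products: exclusion criterion 1 and Table 6-3 list them, with the dose limits. SAP 2.4.2 does not say that the C10 rule sets the intercurrent-event flag.

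The rule as written therefore imputes a Day 150 value that follows a stopped course. An analyst who kept it would depart from the text.

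**4. Size.** Planning inputs from Protocol 12.8.1 and SAP 3.1: 280 completers at 2:1:1 (140/70/70), SD 30, difference 20 against ezetimibe or 40 against placebo, one-sided 0.0125.

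The plan's own figures: SE = 30 × √(1/140 + 1/70) = 4.39. Power for 20 points is 98.96% by the normal approximation and 98.88% by the noncentral t, in line with the stated 99% apart from rounding. Power for 40 points exceeds 99.99%. 280/(1 − 0.06) = 298, consistent with about 300.

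The documents do not give the frequency of LLT use. Assume 1, 2 or 4 of 70 comparator completers have a stopped course, and take the extreme case in which their Day 150 values are lost completely:

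| Comparator n | SE | Increase | Power for 20 points (t) |
|---|---|---|---|
| 70 | 4.39 | – | 98.9% |
| 69 | 4.41 | 0.5% | 98.8% |
| 68 | 4.43 | 1.0% | 98.7% |
| 66 | 4.48 | 2.0% | 98.6% |

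This overstates the cost, because the imputation model uses baseline and available post-baseline values.

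For the opposite choice, suppose k of 75 comparator participants kept Day 150 values that carried a residual LLT effect of r points. The arm mean would shift by k × r/75: 1 × 5/75 = 0.07; 5 × 10/75 = 0.67; 10 × 20/75 = 2.67 points. Both k and r are assumptions. Even the largest shift is small against planned differences of 20 and 40 points.

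**The case for a change.** The strongest case for a change is that the documents do conflict. Section 4 is inaccurate as written, and the protocol lists deviations and prohibited medications as separate outputs, so the deviation table cannot be presumed to replace the missing one. The general tables do not mark which drugs were prohibited. For the estimand, the protocol deferred details to the SAP, stopped courses are foreseeable from the protocol's own instruction to sites, and one sentence confirming the intended handling would cost almost nothing.

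The factual part stands: one protocol-planned summary is not carried over, and Section 4 does not mention it or the reworded definition. But the SAP's silence does not withdraw the protocol commitment, and the protocol prescribes no particular layout.

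The estimand part does not stand as a gap, because a general rule without exceptions covers the stopped course. The alternative, keeping Day 150 values after a long enough interval off LLT, is a trade-off. It would retain some observed data, but it needs reliable stop dates and a washout length for analysis that the documents do not set. The 90-day interval is an eligibility criterion. It also fits less directly with a scenario in which other LLT was never available.

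**Conclusion.** No change to the plan follows. The missing prohibited-medication summary and the no-change statement in SAP Section 4 are a clerical mismatch in descriptive reporting. Analysts can meet the protocol commitment from data already collected, and no efficacy or safety estimate depends on it. The stopped-course question is answered by SAP 2.5.3 as written: values after any LLT use are imputed in the Monotherapy Estimand. The Treatment-policy Estimand uses data collected after LLT, so the question does not arise there.

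Under the assumed 1 to 4 affected of 70 comparator completers, the standard error rises by at most 2.0%, and power against ezetimibe falls by at most about 0.3 percentage points. This rests on LLT use being infrequent. The documents give no rate, but the population does not require LLT under the guideline the protocol cites, post-randomization lipid results are blinded, and users of most LLTs are asked to stop.

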2.5 Analysis supporting primary objective(s)

The primary aim of the study is to demonstrate the superiority of inclisiran to either placebo or ezetimibe in reducing LDL-C.

The FAS will be used for the primary efficacy analysis.

2.5.1 Primary endpoint(s)

The primary endpoint of the study is the percentage change from baseline to Day 150 in LDL-C. .

2.5.2 Statistical hypothesis, model, and method of analysis

The primary objectives are to demonstrate the superiority of inclisiran as monotherapy compared to the use of placebo or ezetimibe separately, in reducing LDL-C as measured by percentage change from baseline to Day 150. To this end, the Monotherapy Estimand assesses the treatment effect of inclisiran alone in the absence of confounding factors such as additional LLT.

As described in [Section 1.2.1](#), in addition to the primary Monotherapy Estimand, the Treatment-policy Estimand was added for regulatory purposes. Both estimands will be considered in parallel as primary analysis.

The primary statistical hypotheses to be tested are:

- $H_{IPO}: \mu_i - \mu_p \geq 0$ vs. $H_{Ipa}: \mu_i - \mu_p < 0$
- $H_{IEO}: \mu_i - \mu_e \geq 0$ vs. $H_{Iea}: \mu_i - \mu_e < 0$

where μ_i , μ_p and μ_e are the mean percentage changes in LDL-C from baseline to Day 150 in the inclisiran group, placebo group, and ezetimibe group respectively. The study can be claimed a success if at least one of the above two individual hypotheses is rejected.

The primary efficacy endpoint will be analyzed using an Analysis of Covariance (ANCOVA) model with treatment, stratification factor, and baseline value as fixed effects. Due to probable heterogeneity of variances between treatment groups, an ANCOVA model that assumes unequal variances between treatment groups will be used. The two primary endpoint hypotheses will be tested using an equally weighted Dunnett test ([Dunnett 1955](#)).

A multiple comparison procedure (MCP) will be used in statistical hypothesis testing for primary and secondary endpoints to control the overall type I error rate at 0.025 (one-sided test). For each of the secondary efficacy endpoints, the Treatment-policy Estimand and the Monotherapy

Estimand will be defined in a similar way as for the primary endpoint, and the MCP will be applied to Monotherapy Estimands and Treatment-policy Estimands separately, to control the overall type I error rate within each set of estimands. Since the Treatment-policy Estimands are intended for regulatory purposes, while the Monotherapy Estimands are intended for all other purposes, no multiplicity adjustment will be made across those two sets of estimands. The testing procedure to be followed is graphically presented in [Figure 2-1](#), and outlined in the following steps:

- First, a weighted Dunnett test with equal weights assigned to each of the two individual primary hypotheses (H_{IP0} and H_{IE0}) is performed. This test will exploit the correlation of the primary endpoint between the two comparisons, with the test statistics derived from the ANCOVA model described as above.
- If one primary hypothesis is rejected, a fraction of its significance level will be passed to the other primary hypothesis while the remaining alpha will be propagated to the family of secondary hypotheses under the same treatment comparison, according to the pre-specified weights as indicated in the graph. The choice of weights for passing alpha to the other primary hypothesis (0.4 and 0.6 respectively) reflects the importance of demonstrating efficacy in the comparison between inclisiran and placebo.
- Within a family of secondary hypotheses (H_{IPk} or H_{IEk}), the hierarchical testing procedure will be used. Refer to [Section 2.6.2](#) for details.
- If one secondary hypothesis in the comparison between inclisiran and placebo H_{IPk} is rejected, a fraction of its significance level will be passed to the next hierarchy of secondary hypotheses under the same treatment comparison, while the remaining alpha will be propagated to the primary hypothesis comparing inclisiran and ezetimibe. If there is no next hierarchy of secondary hypotheses, then the whole alpha will be propagated to the primary hypothesis comparing inclisiran and ezetimibe. Vice versa for the alpha passing from H_{IEk} .

The nodes H_{IP} and H_{IPk} represent the null hypotheses related to the primary and secondary endpoints compared between inclisiran and placebo, while the nodes H_{IE} and H_{IEk} represent the null hypotheses related to the primary and secondary endpoints compared between inclisiran and ezetimibe. The correlations between endpoints and between the two comparisons for each endpoint will also be considered.

The least squares means for the difference between inclisiran and two comparators and corresponding unadjusted two-sided confidence intervals (CI) will be provided separately. The raw p-value for testing the individual hypothesis will also be provided. The superiority of inclisiran to a comparator can be claimed when the corresponding individual null hypothesis is rejected or the raw p-value is statistically significant at corresponding alpha level of current stage.

Details of MCP implementation are described in SAP [Appendix 5.4](#).

2.5.3 Handling of intercurrent events

The Monotherapy Estimand will account for different intercurrent events as explained in the following:

- **Discontinuation of study treatment:** Discontinuation of study treatments will be treated in a hypothetical scenario of what would happen if the participants had not discontinued study treatments (hypothetical strategy).
- **Death:** Participants who die will be treated in a hypothetical scenario of what would happen if participants had not died (hypothetical strategy).
- **Use of lipid-lowering therapy:** Use of LLT will be treated in a hypothetical scenario of what would happen if other LLT were not available (hypothetical strategy).

The efficacy endpoints after the intercurrent events will be multiply imputed under the missing-at-random (MAR) assumption. In other words, it is assumed that a subject who experienced intercurrent events would have had similar efficacy compared to subjects with the same observed covariates in the same treatment group but did not experience any intercurrent event, in a hypothetical scenario that the subject had not experienced any intercurrent event. The imputation model will include stratification factor, baseline value, and available post-baseline values as covariates.

The Treatment-policy Estimand will account for intercurrent events as follows:

- **Discontinuation of study treatment:** Retrieved dropout (RDO) data collected after discontinuation from study treatments will be used for the analysis (treatment-policy strategy). Missing data after discontinuation from study treatments will be multiply imputed based on RDO data, and when there are no sufficient RDO data, a placebo-based Pattern-Mixture Model (PMM) will be used for multiple imputation, which includes stratification factor, baseline value, and available post-baseline values as covariates.
- **Death:** A composite variable strategy will be utilized to handle the intercurrent event of death, and efficacy parameter measurements after death will be imputed using the participant's baseline values.
- **Use of lipid-lowering therapy:** The data collected after use of other LLTs will be used for analyses (treatment-policy strategy). Missing data will be multiply imputed using a placebo-based PMM, which includes stratification factor, baseline value, and available post-baseline values as covariates.

The primary analysis will be conducted on each multiply imputed dataset, and the treatment effects estimated from each of those imputed datasets will be combined using Rubin's method ([Rubin 1987](#)).

2.5.4 Handling of missing values not related to intercurrent event

In the Monotherapy Estimand, missing values not related to intercurrent events will be multiply imputed under the MAR assumption. The imputation model will include stratification factor, baseline value, and available post-baseline values as covariates.

In the Treatment-policy Estimand, missing values not related to intercurrent events will be multiply imputed using a placebo-based PMM, which includes stratification factor, baseline value, and available post-baseline values as covariates.

The primary analysis will be conducted on each multiply imputed dataset, and the treatment effects estimated from each of those imputed datasets will be combined using Rubin's method ([Rubin 1987](#)).

2.5.5 Sensitivity analyses

The following sensitivity analyses will be conducted to assess the robustness of the inferences to various assumptions about the missing data:

- Conduct the primary analyses under the alternative missing value imputation model where the post-baseline (Day 30 and Day 90 visit) measurements are not included as covariates.
- Tipping point analyses: a tipping point analysis will be performed to search for the tipping point that reverses the study conclusion regarding the primary endpoint. In the tipping point analysis, scale-adjustments will be applied to the imputed values in the inclisiran arm. The multiplicity adjustment between the inclisiran vs. placebo and inclisiran vs. ezetimibe comparisons will be performed using the same graphical approach as outlined in [Section 2.5.2](#), but the graph in [Figure 2-1](#) is reduced using Algorithm 1 in [Bretz et al 2011](#) to only include the two hypotheses regarding the primary endpoint. In the reduced graph, the initial weights are 1/2 for each of the two hypotheses, with transition weight = 1 between them.

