### **9.1.2 Discontinuation from study**

Discontinuation from study is when the participant permanently stops receiving the study treatment, and further protocol-required assessments or follow-up, for any reason.

If the participant agrees, a final evaluation at the time of the participant's study discontinuation should be made as detailed in the assessment table (refer to [Section 8](#)).

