#### **12.4.5 Sensitivity analyses**

Sensitivity analyses such as tipping point analyses will be conducted to assess the robustness of the inferences to various assumptions about the missing data, and details will be provided in the SAP.

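### Does the Treatment-policy sensitivity plan need to let missing ezetimibe values do better than placebo-based imputation allows?

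*SAP*

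**What the plan says.** For the Treatment-policy Estimand, SAP 2.5.4 states: "In the Treatment-policy Estimand, missing values not related to intercurrent events will be multiply imputed using a placebo-based PMM". Protocol 12.4.4 has the same rule. Neither names or exempts an arm. The model includes the stratification factor, baseline and available post-baseline values.

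The category is narrow. Protocol 9.1.2 says: "Discontinuation from study is when the participant permanently stops receiving the study treatment, and further protocol-required assessments or follow-up, for any reason". Leaving the study therefore counts as stopping treatment and falls under SAP 2.5.3, where "Missing data after discontinuation from study treatments will be multiply imputed based on RDO data", with the placebo-based model as the fallback. What remains for 2.5.4 is mainly participants still on treatment without a usable Day 150 sample.

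SAP 2.5.5 lists two sensitivity analyses. One repeats the primary analyses with an imputation model "where the post-baseline (Day 30 and Day 90 visit) measurements are not included as covariates". The other is a tipping point analysis: "In the tipping point analysis, scale-adjustments will be applied to the imputed values in the inclisiran arm". For the multiplicity step of that analysis, "In the reduced graph, the initial weights are 1/2 for each of the two hypotheses, with transition weight = 1 between them".

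For the parallel primary estimand, SAP 2.5.4 states: "In the Monotherapy Estimand, missing values not related to intercurrent events will be multiply imputed under the MAR assumption".

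**The concern.** Placebo-based imputation is usually chosen because it is hard on the experimental arm. Applied to an active comparator, it also removes part of the comparator's effect and so can widen the difference in favour of the experimental drug. Inclisiran versus ezetimibe is one of two primary hypotheses, and rejecting either one is enough to claim success (SAP 2.5.2).

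The sensitivity analyses would normally expose such a dependence. Here the first moves imputed ezetimibe values further towards placebo, and the second never touches the ezetimibe arm. Protocol 12.4.5 promises more: "Sensitivity analyses such as tipping point analyses will be conducted to assess the robustness of the inferences to various assumptions about the missing data". If ezetimibe participants were missing much more often than inclisiran participants, the superiority claim could rest partly on an assumption about the comparator that no listed check varies in the comparator's favour.

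**Working it through.** **Inputs from the plan** (Protocol 12.8.1, SAP 3.1): differences of 40 points versus placebo and 20 versus ezetimibe, SD 30, one-sided 0.0125, 280 completers at 2:1:1, 6% dropout, about 300 randomized (150/75/75). Recomputed power for 20 points with 140 versus 70 completers is 98.96% (normal) or 98.88% (noncentral t), in line with the stated 99% apart from rounding. 280/0.94 = 298, in line with about 300.

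**Assumptions.** The documents give no missing rate for this category. Let m_i and m_e be the missing shares for inclisiran and ezetimibe, and c the share of an arm's own effect that the Day 30/90 covariates carry into its imputed values. The planned differences imply arm means of −40, −20 and 0 if placebo is set at 0.

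**Shift of the contrast under the planned rule**

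Contrast = −40[1 − m_i(1−c)] + 20[1 − m_e(1−c)], so the shift from −20 is (1−c)(40 m_i − 20 m_e). It is zero at m_e = 2 m_i for any c below 1. A negative shift favours inclisiran.

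| m_i / m_e | c = 0 | c = 0.5 | c = 0.8 |
|---|---|---|---|
| 2% / 2% | +0.40 | +0.20 | +0.08 |
| 1% / 5% | −0.60 | −0.30 | −0.12 |
| 0% / 4% | −0.80 | −0.40 | −0.16 |

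The column c = 0 also describes the first sensitivity analysis, which drops the post-baseline covariates. For the planned rule it is an upper limit. In a simulation of a placebo-fitted regression, the mean imputed ezetimibe value was −9.2, −13.2 and −16.4 at visit correlations of 0.3, 0.5 and 0.7, so c is about 9.2/20 = 0.46, 0.66 and 0.82. Without Day 30/90 it was about 0.

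A separate simulation of 4,000 trials (150/75/75, Day 90–150 correlation 0.5 or 0.8) agrees. Planned rule: +0.21 or +0.08 at 2%/2%, −0.31 or −0.12 at 1%/5%, −0.38 or −0.17 at 0%/4%. Without the covariate, the largest shift was −0.82 (Monte Carlo SE at most 0.016).

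**Distance to reversal**

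SE = 30 × √(1/150 + 1/75) = 4.24.

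- One-sided 0.0125: 20 − 2.241 × 4.24 = 10.5 points.
- One-sided 0.025, the level once the placebo hypothesis is rejected in the reduced graph: 20 − 1.960 × 4.24 = 11.7 points.

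The largest favourable shift, 0.8, is about 8% of the smaller margin (0.8/10.5).

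**If ezetimibe followed its own arm and inclisiran stayed placebo-based** (c = 0), the contrast would be −40(1 − m_i) + 20: −19.2 at 2%/2%, −19.6 at 1%/5% and −20.0 at 0%/4%. Even at 6% missing in both arms it would be −17.6, with power 97.2% at 150 versus 75.

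**What varying ezetimibe would add to the tipping point.** Take 1%/5% missing plus a further 3% per arm imputed after intercurrent events, so 4% and 8% imputed, all at 0% change, with scaling applied to LDL-C. The starting contrast is −40 × 0.96 + 20 × 0.92 = −20. Scaling by k moves an imputed value to 100(k − 1)% change and multiplies its SD by k. The arm variance grows and must be re-estimated, because the ANCOVA allows unequal variances. At inclisiran factor k:

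- mean = −38.4 + 4(k − 1)
- variance = 0.96(900 + 1600) + 0.04[900k² + 10000(k − 1)²] − mean²

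With ezetimibe unscaled (mean −18.4, variance 929), the contrast plus 1.96 SE reaches zero at k = 3.06: mean −30.15, variance 3531, SE = √(3531/150 + 929/75) = 5.99, and −30.15 + 18.4 + 1.96 × 5.99 = 0. The same calculation with ezetimibe values scaled by 0.8 and 0.6 gives 2.83 and 2.56. The tipping factors are thus about 3.1, 2.8 and 2.6. Holding the SE at 4.24 would give 3.9, 3.5 and 3.1, which is too lenient.

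**The case for a change.** The best argument for a change is that a one-arm tipping factor says nothing direct about ezetimibe. To match the move to own-arm imputation for ezetimibe, each imputed inclisiran value must worsen by 20(1−c)m_e/(m_i + x), where x is the share imputed after intercurrent events. At an assumed x of 3% and c from 0.8 down to 0, that is 1.6 to 8 points (2%/2%), 5 to 25 (1%/5%) or 5.3 to 26.7 (0%/4%). A reader cannot make that conversion unaided, and with very few imputed inclisiran values the analysis has little leverage. The Monotherapy analysis also changes the intercurrent-event strategies, so it does not isolate this rule. Extra runs would be cheap and need no protocol amendment.

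All of this is true as description, but it does not show a gain. The contrast is a single difference: worsening inclisiran and improving ezetimibe move its mean the same way, and the planned search continues until the conclusion reverses. In the example, the inclisiran factor stays at about 2.6 even when ezetimibe values are scaled to 0.6, so imputed LDL-C would still have to be some two and a half times baseline. The unfavourable case needs on-treatment Day 150 samples to be lost more than twice as often on ezetimibe. Treatment is double-dummy and post-randomization lipids are masked (Protocol 6.5, 8.3), and nothing in the documents suggests a mechanism for that; 0%/4% means 0 of 150 against 3 of 75 participants.

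The obvious additions also bring difficulties:

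- Scaling all imputed ezetimibe values would credit participants who died, whose values SAP 2.5.3 sets to baseline as an unfavourable outcome, with a reduction.
- Factors of 0.8 and 0.6 correspond to 20- and 40-point effects only at c = 0. At c = 0.5 the imputed value is −10%, and 0.8 × 90 = 72, a 28% reduction.
- Own-arm imputation in all arms isolates the rule, but at equal missingness it favours inclisiran slightly more than the plan does, by about 0.1 to 0.4 points at 2%/2%.

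**Conclusion.** No change is needed. The reading of the text is right: no arm is exempt, and neither analysis in SAP 2.5.5 improves missing ezetimibe values. Followed as written, the plan still gives a sound answer on this hypothesis. The rule is conservative for inclisiran unless ezetimibe's missing share exceeds about twice inclisiran's, and the largest favourable shift at the assumed rates is 0.8 points against 10.5 to 11.7 needed for reversal. The planned tipping point attacks the same difference, and a co-primary analysis already imputes ezetimibe from its own arm.

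This rests on assumed missing rates of up to 5% in a category for which the documents give none, on the planning means and SD, and on an observed contrast near 20 points. A much smaller contrast would shrink the margin, but the planned tipping point would then tip at a factor closer to 1 and show it, provided some inclisiran values are imputed. A two-way version for the Treatment-policy Estimand, excluding values set to baseline after death and re-estimating variances at each grid point, would be an optional extra rather than a correction.
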